## **5.6 Safety Analysis**

Overall safety summaries and listings will be performed using the SS-r. AE tables will be summarized using SS-t.

### **5.6.1 Extent of Exposure**

Administration of treatments will be listed by participant and planned treatment sequence. The listing will include the actual and planned treatment received, start and stop date and time of drug administration, total volume of treatment given, and site of injection (L/R side of the body and upper/lower abdomen).

Study medication duration will be calculated in two ways:

- For the entire study duration (in days):
  - Calculated as the date of last dose of IMP (including Run-Out) - date of first dose of IMP in the Run-In Period + 1.
- For Treatment Periods 1 and 2 only (in days):
  - Calculated as the date of the last dose of IMP (excluding Run-Out) – date of first dose of IMP in Treatment Period 1 +1.

Study medication durations will be summarized by sequence using descriptive statistics.

An additional summary of the number of infusions received in Treatment Periods 1 and 2 will also be generated. The following summaries will be generated based on the SS-r, by planned treatment sequence:

- Number of infusions received as continuous and using the following categorical values: 1-4, 5-8, 9-12, 13-16, 17-20, and 21-24;
- Number of infusions received excluding mock infusions, using similar approach as the point above.

An additional by participant listing of the exposure to IMP will be generated.

### **5.6.2 Adverse Events**

All AEs will be coded using MedDRA® and characterized as pre-treatment and treatment-emergent according to the intake of each treatment. Adverse events with a start date prior to the first dose of IMP in the Run-In Period will be defined as pre-treatment AEs. A TEAE is defined as any AE with a start date on or after the first dose of IMP in Run-In, and on or before the earliest of the following: the last date of infusion (including Run-Out, if applicable) +56 days, final contact date or death. A TEAE is also defined as any unresolved event already present before administration of treatment that worsens in intensity following exposure to the treatment.

Adverse events will be summarized by treatment period and treatment group based on the SS-t. If a participant receives an incorrect treatment per the randomization schedule, the participant will be excluded from the summaries, and the AEs for this participant will be listed only. In such cases these will be noted in the footnotes for the relevant tables. Pre-treatment AEs will not be included in any summaries.

Adverse events will be assigned to the respective treatment period and treatment group based on the start date of the AE. The assignment of AEs to a given treatment period is summarized in Appendix 4 Section 8.4. The treatment groups will be summarized per treatment period in the following way:

- Run-In:
  - PBO (All 3 sequences)
- Treatment Period 1
  - RLZ (Sequence 1)
  - Pooled PBO (Sequence 2 and 3)
- Treatment Period 2

---

- RLZ/RLZ (Sequence 1)
- PBO/RLZ (Sequence 2)
- PBO/PBO (Sequence 3)
- Run-Out and SFU (pooled)
  - RLZ/RLZ (Sequence 1)
  - PBO/RLZ (Sequence 2)
  - PBO/PBO (Sequence 3)

The total N within the summary tables will correspond to the number of participants randomized to the respective treatment sequence who receive at least one dose of IMP in the given treatment period or who entered the SFU period.

For details regarding partial dates, see Appendix 2 [Section 8.2](#).

The number and percentage of participants who experience TEAEs will be summarized by MedDRA™ SOC, HLT, and PT as described above.

Summaries of TEAEs will include the following:

- Incidence of overall TEAEs (overview including number and percentage of study participant with any TEAEs, serious TEAEs, discontinuations due to TEAEs, permanent withdrawal of study medication due to TEAEs, drug related TEAEs, severe TEAEs and TEAEs leading to death; event counts will also be included)
- Incidence of any TEAEs
- Incidence of any serious TEAEs
- TEAEs leading to permanent withdrawal of IMP
- Incidence of severe TEAEs
- Incidence of treatment-related TEAEs
- Incidence of TEAEs by maximum causal relationship with IMP
- Incidence of TEAEs by maximum intensity
- Incidence of serious TEAEs by maximum causal relationship with IMP
- Incidence of serious TEAEs by causal relationship
- Incidence of fatal TEAEs by causal relationship with IMP
- Incidence of non-serious TEAEs above reporting threshold of 5% of study participants
  - For the purpose of this table, the 5% reporting threshold will be considered based on all TEAEs reported within each of the following groups:
    - PBO Run-In
    - PBO Treatment Period 1
    - RLZ Treatment Period 1

---

- PBO/PBO Treatment Period 2, Run-Out, SFU
- PBO/RLZ Treatment Period 2, Run-Out, SFU
- RLZ/RLZ Treatment Period 2, Run-Out, SFU

ie, non-serious TEAEs occurring with incidence >5% within any of the above groups will be included.

- Incidence of drug-related TEAEs (overview including number and percentage of study participant with any drug-related TEAEs, serious drug-related TEAEs, discontinuations due to drug-related TEAEs, permanent withdrawal of study medication due to drug-related TEAEs, severe drug-related TEAEs and drug-related TEAEs leading to death; event counts will also be included)
- Incidence of drug-related TEAEs by preferred term
- Incidence of serious drug-related TEAEs by preferred term

In summaries including relationship, the following relationships will be summarized: 'Not related', 'Related'. Participants who experience the same event multiple times will be included in the most related category for tabulations by maximum relationship. Events with missing relationship will be considered as 'Related' but recorded as missing in the listings.

In summaries including intensity, the following intensity categories will be summarized: 'Mild', 'Moderate', 'Severe'. Participants who experience the same event multiple times will be included in the most severe category for tabulations by maximum intensity. Events with missing intensity will be considered as 'Severe' events for summary purposes but recorded as missing in the listings.

Adverse event summaries will be sorted in the following way:

- For Run-In:
  - Sort by alphabetical SOC and HLT within SOC. Within SOC and HLT within SOC, sort by descending frequency of PT in Run-In.
- For Treatment Period 1 and Treatment Period 2:
  - Sort by alphabetical SOC and HLT within SOC. Within SOC and HLT within SOC, sort by descending frequency of PT in the RLZ/RLZ (Treatment Period 2) group. In the case of ties, sort these alphabetically within the RLZ/RLZ (Treatment Period 2) group.
- For Run-Out and SFU group:
  - Sort by alphabetical SOC and HLT within SOC. Within SOC and HLT within SOC, sort by descending frequency of PT in the RLZ/RLZ group. In the case of ties, sort these alphabetically within the RLZ/RLZ group

All listings will be presented by planned treatment sequence and will include study participant, SOC/HLT/PT/reported term, the onset date and outcome date of the event, the Treatment Period of onset, most recent actual treatment received, days since the most recent dose (derived), the event duration (derived), days since the first dose in the Run-In Period (derived), days since the first dose in Treatment Period 1 (derived), pattern of event, flag for a serious event, intensity,

relationship, action taken, AESM flag, AESI flag, Adverse Event of Focus (AEOF) flag, and outcome, unless specified.

The following listings of AEs and TEAEs will be provided:

- All AEs
- All TEAEs

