9.1 Definition of analysis sets

The following analysis sets have been defined for this study:

All Study Participants Set: The All-Study Participants Set (ASP) consists of all study participants that sign the informed consent form. This set includes screening failures.

Randomized Set: The Randomized Set (RS) will consist of all participants randomized into the study.

Safety Set – as Randomized: The Safety Set as randomized (SS-r) consists of all study participants who received any study treatment, including during the run-in period. The study participants will be analyzed according to the randomized treatment groups during the specific treatment period.

The SS-r will be used for production of safety analysis by visit, as well as demographics and immunogenicity analyses.

Safety Set – as Treated: The Safety Set as treated (SS-t) consists of all study participants who received any study treatment including during the run-in period. If a participant received at least one dose of active treatment during a given treatment period, participant will be allocated to active treatment group at the given treatment period and any period thereafter in the SS-t as treated analysis set (most conservative approach). For analysis purposes, the SS-t will be used for tabulating AEs by treatment where AEs are assigned to the active treatment group based on the onset of AE relative to the first dose of active treatment.

The SS-t will be used for safety overall analysis.

Full Analysis Set: The Full Analysis Set (FAS) consists of all study participants in the SS-r who have a Baseline value and at least one post-Baseline efficacy endpoint assessment. Study participants who receive at least one dose of treatment not per randomization schedule will be excluded from the FAS.

This analysis set will be used for the summaries and analyses of primary, secondary, and exploratory efficacy variables data.

Pharmacokinetic Set: The Pharmacokinetics Set (PKS) consists of all study participants in the SS-r who have at least one dose of active IMP and at least one measurable PK concentration including below limit of quantification (BLQ). The PKS will be used for all PK summaries and analyses. If a study participant in the PKS is missing individual time points or are otherwise unobservable, they will be included in the PKS but those time points will be omitted from the PK summaries, as appropriate.

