Pharmacodynamic Set: The Pharmacodynamic set (PDS) is a subset of the FAS, consisting of those study participants who had no important protocol deviations affecting the PD variables, as confirmed during a pre-analysis review of the data prior to database lock, and who had at least one valid post-Baseline measurement of serum total IgG and IgG subclasses. The final PDS will be identified after database lock to confirm availability of at least one post-Baseline valid measurement due to blinding. The PDS will be used for all PD summaries and analyses.

Participants who had important protocol deviations affecting the relevant efficacy/PK/PD variables, as confirmed during a pre-analysis review of the data prior to database lock might be excluded from relevant analyses. Such exclusions will be described in tables, figures, and listings (TFLs) and/or the CSR.

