**5.1.2 Changes to Protocol-Defined Analyses**

According to the protocol, the Baseline for each variable will be taken as the value measured prior to, but closest to, the treatment on Day 1 (Visit 3, Week 1). However, this rule is specific to

efficacy endpoint assessments only. For safety variables the Baseline will be the most recent value prior to the first dose in the Run-In period. The Baseline definitions for all endpoints are summarized in [Section 5.1.1.3](#).

According to the protocol, the mean 7-day pain and fatigue scores after 10 weeks of treatment will be used for the secondary efficacy endpoint analysis. However, it has been clarified in the SAP that this is based on 12 weeks of treatment (Visits 3-14 in Treatment Period 1, and Visits 15-26 in Treatment Period 2).

Per the protocol, as a secondary analysis strategy, dropouts will be imputed as if they belong to the placebo group, under the conservative assumptions that dropouts are due to a lack of drug efficacy. This analysis will not be produced for the CSR.

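### SAP 5.6.2 drops anyone given an incorrect treatment from the adverse event tables; the protocol counts that participant as treated, and SAP 5.1.2 does not declare the change

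*SAP*

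**What the plan says.** **Protocol 9.1.** SS-t contains everyone who received any study treatment, Run-In included. After at least one active dose in a period, the "participant will be allocated to active treatment group at the given treatment period and any period thereafter in the SS-t as treated analysis set", which the protocol calls the most conservative choice. For tabulation by treatment, "AEs are assigned to the active treatment group based on the onset of AE relative to the first dose of active treatment".

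The protocol does exclude people for off-schedule dosing, but from a different set: "Study participants who receive at least one dose of treatment not per randomization schedule will be excluded from the FAS". The Pharmacodynamic Set is a subset of the FAS, so it inherits that exclusion. The general clause on deviation-based exclusions covers "Participants who had important protocol deviations affecting the relevant efficacy/PK/PD variables" and does not mention safety. SAP 4 repeats that clause.

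**SAP 4.** SS-t has the same membership as in the protocol. The allocation rule is gone, and the reader is sent to 5.6.2.

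**SAP 5.6.2.** Adverse event summaries are said to rest on SS-t. If a participant receives an incorrect treatment, "the participant will be excluded from the summaries, and the AEs for this participant will be listed only". The section adds that "In such cases these will be noted in the footnotes for the relevant tables". The table denominator is given as "number of participants randomized to the respective treatment sequence who receive at least one dose of IMP in the given treatment period"; participants entering follow-up are also counted.

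**SAP 5.1.2,** headed "Changes to Protocol-Defined Analyses", lists three items: the Baseline definition, the timing of the pain and fatigue scores, and the dropped placebo-based imputation.

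**The concern.** SS-r and SS-t have identical membership. They differ only in how a participant dosed off-schedule is allocated. If those participants are removed, the as-treated set has nothing left to do, and tables labelled SS-t will not contain all of SS-t.

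The exclusion is broad. It is not confined to the period of the error, and it works in both directions: a Sequence 1 participant given one placebo infusion by mistake also leaves the tables.

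Occurrence of TEAEs is a secondary endpoint. An event that follows unplanned active exposure is one an as-treated analysis is meant to count under active, and here it would be counted nowhere. The loss would reach the 5.6.2 incidence tables and the registry tables in SAP 6.1 that use SS-t. Incorrect treatment is a foreseen event, since both documents make it a category of important protocol deviation.

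**Working it through.** The plan states no figure to reproduce, so the check compares the rules and then works two examples.

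**The rules side by side, for a participant who receives at least one infusion of the wrong treatment**

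| | Protocol 9.1 | SAP 5.6.2 |
|---|---|---|
| Member of SS-t | Yes | Yes (SAP 4) |
| Counted in AE tables | Yes, under active after any active dose | No, listed only |
| Period affected | Active for that period and later ones | Not limited to any period |
| Denominator | As-treated allocation | By randomized sequence; no stated exception for excluded participants |

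The documents agree on who belongs to SS-t. They disagree on whether such a participant is tabulated, and both rules cannot be applied to the same person.

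**How little triggers it.** Planned infusions per participant: 2 (Run-In) + 12 + 12 + 2 (Run-Out) = 28. One wrong infusion is 1/28 = 3.6% of them.

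**Registry tables.** SAP 6.1 lists seven. Four use SS-t: the TEAE overview, non-serious TEAEs above 5%, serious TEAEs and fatal TEAEs. Three use the Randomized Set: disposition, demographics and discontinuation due to AEs.

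**Examples.** Inputs: 20 per sequence (protocol synopsis and 4.1), so in Period 1 active N = 20 and pooled placebo N = 40. Assumption: one misdosed participant, who has the only serious TEAE of Period 1.

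(a) A Sequence 3 participant receives one active dose in error and then has the event.
- Protocol: active 1/(20 + 1) = 1/21 = 4.8%.
- SAP: active 0/20 = 0%. Placebo is 0/39 if the participant leaves the denominator, or 0/40 if the N rule is read literally.

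(b) A Sequence 1 participant receives one placebo dose in error and has the event after the first active dose.
- Protocol: active 1/20 = 5.0%.
- SAP: active 0/(20 − 1) = 0/19 on the plain reading of exclusion, or 0/20 on the literal N rule. Both are 0%.

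In each case the only serious event on active becomes zero incidence.

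**The case against.** The strongest reply is that the SAP is entitled to do this and does it openly. SAP 1 says the protocol governs unless the SAP specifies otherwise, SAP 4 refers to 5.6.2 for the use of SS-t, and 5.6.2 states the exclusion and its footnote plainly. That is right, but it means the exclusion is what will be programmed. It does not supply a reason, and 5.1.2 is the place where such a change should be visible. The amendment log in SAP 9.1 records only clarifications to the SS-t definition and to the table requirements, without naming the exclusion.

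Second, the data are not lost. Events stay in the listings with the actual treatment shown, the tables carry a footnote, important deviations are summarized by treatment group and period (5.1.3), dosing deviations are described in the CSR (5.4), and discontinuations due to AEs are tabulated on the Randomized Set. Laboratory, vital-sign and liver summaries stay on SS-r. All of this stands and limits the severity. It does not restore a numerator or a denominator.

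Third, SAP 5.7 tabulates TEAEs on SS-r by ADA category, so the event in example (b) would still appear there. That is so, but those tables omit Sequence 3, and hence example (a). They are split by ADA status, and they do not change the 5.6.2 or registry incidence.

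Fourth, the protocol rule is itself incomplete. It does not settle mixed exposure within a period. Its carry-forward would also count a Sequence 3 participant as active throughout a placebo-only Period 2 after a single error in Period 1. This is fair, and the fix has to address it. It is a reason to complete the rule, not to drop the participant.

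**Conclusion.** The concern holds. SAP 5.6.2 reverses the protocol's handling of incorrectly treated participants in the adverse event tables, and 5.1.2 does not declare it. This is a wrong rule, not a missing detail, and it should be fixed.

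Its size depends on a dosing error, for which the documents give no rate, so no probability is claimed. If one occurs, a sole serious event on active could be reported as 0% where the protocol's rule gives 4.8% or 5.0%. Those figures assume 20 per sequence and that the misdosed participant has the only serious TEAE in the period. The consequence is confined to summary tables, including four registry tables. The efficacy analyses are not touched by this rule.

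**What to change.** **Preferred.** Delete the exclusion sentence in SAP 5.6.2, restore the protocol's as-treated allocation in SAP 4 and 5.6.2, and apply it to every adverse event table on SS-t. Then:

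- Define the table N by the same as-treated allocation as the numerator.
- State one rule for a participant with both placebo and erroneous active exposure in a period. Either count the participant under active for the whole period (example (a): active N = 21, placebo N = 40 − 1 = 39), or count the participant in both columns with events split at the first active dose (active N = 21, placebo N = 40).
- Name the active column to be used in later periods, and say how an active dose in Run-In is shown, since that period has only a placebo column.
- Keep the footnote.

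**If the sponsor keeps the exclusion.** Declare and justify it in SAP 5.1.2, and add an as-treated TEAE table that contains these participants and includes serious and fatal events.

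**Cost.** The preferred route needs revised text in SAP 4 and 5.6.2, an as-treated group variable by period in the adverse event analysis dataset, and adjusted table shells. The alternative needs one paragraph and one supplementary table. Neither needs new data, because SAP 5.6.1 already lists the actual treatment received.

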## 8.4 Appendix 4: Period of Onset Assignment

### 8.4.1 Adverse Events and IPDs

The period of onset for AEs and IPDs is determined in the following way:

- If the event occurs prior to the date of first dose of IMP in Run-In, then the event is assigned to the Screening Period.
- Events are assigned to the Run-In Period in the following cases:
  - If the event occurs on or after the date of first dose of IMP in Run-In and prior to the date of first dose of IMP in Treatment Period 1.
  - If the study participant withdraws during Run-In (ie prior to the first dose of IMP in Treatment Period 1) and the event occurs on or after the date of first dose of IMP in Run-In and within 6 days after the date of last dose of IMP prior to withdrawal.

- Events are assigned to Treatment Period 1 in the following cases:
  - If the event occurs on or after the date of first dose of IMP in Treatment Period 1 and prior to the date of first dose of IMP in Treatment Period 2.
  - If the study participant withdraws during Treatment Period 1 (ie prior to the first dose of IMP in Treatment Period 2) and the event occurs on or after the date of first dose of IMP in Treatment Period 1 and within 6 days after the date of last dose of IMP prior to withdrawal.
- Events are assigned to Treatment Period 2 in the following cases:
  - If the event occurs on or after the date of first dose of IMP in Treatment Period 2 and prior to the date of first dose of IMP in Run-Out.
  - If the study participant withdraws during Treatment Period 2 (ie prior to the first dose of IMP in Run-Out) and the event occurs on or after the date of first dose of IMP in Treatment Period 2 and within 6 days after the date of last dose of IMP prior to withdrawal.
- Events are assigned to the Run-Out Period in the following cases:
  - If the event occurs on or after the date of first dose of IMP in Run-Out and within 6 days after the date of last dose of IMP in Run-Out.
- Events are assigned to the SFU in the following case:
  - If the event occurs on or after 7 days after the date of last dose of IMP.

For AEs, the above rules are applied after any date imputation.

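### SAP 5.6.2 and 8.4.1 do not place adverse events that become treatment-emergent by worsening: read literally, some leave every table and others stay only in a placebo column

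*SAP*

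**What the plan says.** SAP 5.6.2 gives two routes to a treatment-emergent adverse event (TEAE). The first is a start date on or after the first Run-In dose and inside the follow-up window. The second concerns worsening: "A TEAE is also defined as any unresolved event already present before administration of treatment that worsens in intensity following exposure to the treatment".

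The same section defines a class that must stay out of the tables. "Adverse events with a start date prior to the first dose of IMP in the Run-In Period will be defined as pre-treatment AEs", and "Pre-treatment AEs will not be included in any summaries".

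For placement in a column, the rule is "Adverse events will be assigned to the respective treatment period and treatment group based on the start date of the AE". SAP 8.4.1 turns this into period limits. For the earliest events, "If the event occurs prior to the date of first dose of IMP in Run-In, then the event is assigned to the Screening Period". An event belongs to Treatment Period 1 if it occurs from the first Period 1 dose and "prior to the date of first dose of IMP in Treatment Period 2". No line in 8.4.1 mentions worsening.

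The table columns in 5.6.2 begin at Run-In (placebo, all sequences). Period 1 has RLZ and Pooled PBO. Period 2, and then Run-Out with follow-up, have RLZ/RLZ, PBO/RLZ and PBO/PBO. There is no Screening column.

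Protocol 9.1, on the as-treated safety set, also works from onset: "AEs are assigned to the active treatment group based on the onset of AE relative to the first dose of active treatment".

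**The concern.** The TEAE definition admits events by worsening, but nothing in the placement rules recognises the date of worsening. Occurrence of TEAEs is a secondary endpoint, and the incidence tables are where it is reported.

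Two consequences follow if the rules are programmed as written. First, an event that starts in Screening and worsens after dosing meets one definition that puts it into the tables and another that keeps it out. No precedence is given, so two programmers could produce different tables. Second, an event that starts on placebo, is unresolved at the switch to rozanolixizumab and then worsens under the same record is credited only to placebo. If the record holds the highest intensity reached, a severity reached on rozanolixizumab could appear under placebo in the severe and maximum-intensity tables.

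**Working it through.** The plan states no figure on this point, so there is none to reproduce. The check applies the SAP rules to example events and then sizes one misplacement.

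**Inputs.** First doses fall on planned Day -14 (Run-In), Day 1 (Period 1), Day 85 (Period 2) and Day 169 (Run-Out), from SAP 5.1.1.2. Each sequence has 20 planned participants (SAP 1.2), so Pooled PBO in Period 1 has 20 + 20 = 40. The start and worsening days below are chosen only to exercise the rules.

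**Trace.**

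| Sequence | Start day | Worsening day | Column by start date | Column at worsening |
|---|---|---|---|---|
| 1 | -20 | 10 | none (Screening) | RLZ, Period 1 |
| 1 | -5 | 10 | PBO, Run-In | RLZ, Period 1 |
| 2 | -20 | 90 | none (Screening) | PBO/RLZ, Period 2 |
| 2 | 60 | 90 | Pooled PBO, Period 1 | PBO/RLZ, Period 2 |
| 3 | 60 | 90 | Pooled PBO, Period 1 | PBO/PBO, Period 2 |
| 2 | -5 | 10 | PBO, Run-In | Pooled PBO, Period 1 |
| 1 | 60 | 90 | RLZ, Period 1 | RLZ/RLZ, Period 2 |

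In the first four rows a worsening on rozanolixizumab is missing from the rozanolixizumab columns. Rows five and six move between placebo columns, and row seven between active columns. No row moves from active to placebo, because the design has no such switch between treatment columns: Run-Out dosing is placebo, but its tables keep the sequence labels. The planned switches from placebo to active involve Sequences 1 and 2, which is 20 + 20 = 40 of 60 participants.

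**Size of one misplacement.** The shift is k/n, where k counts affected participants with no other TEAE in the same row of the same column.

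- PBO/RLZ, Period 2: 1/20 = 5.0 points. RLZ, Period 1: also 1/20 = 5.0 points.
- If all 25% planned dropout came before Period 2, n = 20 × 0.75 = 15 and the shift is 1/15 = 6.7 points.
- The documents give no frequency of worsening. Over an assumed range of k = 0 to 4 at n = 20, the shift is 0 to 20 points. That range only shows the scale.
- In a severe-intensity row, one record that holds the later intensity adds 1/40 = 2.5 points to Pooled PBO and removes 1/20 = 5.0 points from PBO/RLZ.
- The non-serious table admits a term when incidence is strictly above 5% in any listed group. With 20 in the PBO/RLZ group, 2/20 = 10% meets this and 1/20 = 5.0% does not. Another group may still bring the term in.

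**How worsening is recorded.** Protocol 8.3.1 requires AEs that worsen after the first visit to be reported, but does not say whether as a new record. Protocol Appendix 3 sends follow-up information to the form first completed. Neither document says that a rise in intensity opens a new record with a new start date. If it always did, the worsening part of the TEAE definition would be largely redundant.

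**The case against.** The strongest reply is that the gap may be closed at data entry. Protocol 10.1.6.1 refers to CRF Completion Guidelines, which are not part of these documents. Several passages lean towards separate records: Appendix 3 counts a flare of a pre-existing condition as an AE and has the investigator give each AE one intensity category, and Protocol 8.2.1 records worsened examination findings as AEs. The SAP listings carry one intensity per event. This stands as a limit on the point. It covers much worsening of medical history, but it does not settle what happens to an AE already on record.

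A reader might infer that headache is the main casualty, since it is the most commonly reported reaction and is also anticipated in this population. The documents do not support that for headache known from medical history: its worsening on drug would be a new AE with onset on drug. Severe or serious headache is also listed and summarised separately (SAP 5.6.4). Only a headache already recorded as an AE and still unresolved is exposed.

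It is also fair that the protocol itself chose attribution by onset, and that the rule is symmetric in form. It also displaces placebo-to-placebo worsening, as the Sequence 3 row shows. Other SAP choices go the other way: partial AE dates are imputed to Period 2 first (SAP 8.2.1), and Run-Out and follow-up events stay under the sequence labels. The listings keep every event. What survives is that neither onset rule says what to do with an event that qualifies only by worsening, and that treatment changes between columns go in one direction.

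**Conclusion.** The inconsistency is real and lies in the SAP's own wording. For Screening-onset events it is a direct conflict between inclusion and exclusion. For events carried across a placebo-to-rozanolixizumab switch, it is an attribution rule that ignores the worsening which the TEAE definition was written to capture. The likely direction is understatement of rozanolixizumab TEAEs.

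Three stronger readings are tempting and not supported.

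- That rozanolixizumab TEAEs will be undercounted. This depends on recording practice, and the effect is nil if each worsening is a new record.
- That Screening-onset events are counted under Screening. They have no column and would appear in no summary.
- That a particular undercount, such as 5 to 10 points, can be predicted. Only the unit is known: 5 points per affected participant at n = 20, provided that the participant has no other TEAE in that row. For the any-TEAE row over 12 weekly infusions, the shift could be nil.

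**What to change.** Make the change by SAP amendment before the unblinding for the Early Readout Analysis. SAP 1 calls for an amendment when the method for a secondary endpoint changes before unblinding.

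1. Require any increase in intensity of a recorded AE to be entered as a new AE record with its own start date. Where one record already holds the worsening, count it as a TEAE in the period and treatment group at the date of worsening. Keep any onset after the first Run-In dose in its own period, at the intensity it had then. Simply replacing the onset date would remove a genuine placebo-onset TEAE from the placebo column, so the event should count in both places.
2. Exempt events that qualify by worsening from the rule that "Pre-treatment AEs will not be included in any summaries".
3. Amend 5.6.2 and 8.4.1 together so that TEAE status, period and treatment group use the same date.

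The cost is SAP wording, a small derivation, and a CRF completion note or site query to obtain the date of worsening and the earlier intensity where one record covers both. The documents do not show that this date is collected, so some queries may be needed.
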